1 SYNOPSIS/SUMMARY

TITLE: Myotonia, muscle stiffness and elasticity in neuromuscular disorders
PROTOCOL NO.: Myotonia and Stiffness in NMD V1 [01. July 2019]

INVESTIGATOR STUDY SITE: Friedrich-Baur-Institute, Department of Neurology, Klinikum der Universität München. [name], Germany

OBJECTIVES: The primary objective of this study is to assess stiffness, muscle tone, relaxation periods and elasticity of various muscles in patients with dystrophic or non-dystrophic myotonia. The secondary objectives are (1) to provide reference values for stiffness, muscle tone, relaxation periods and elasticity of various muscles in patients with dystrophic or non-dystrophic myotonia; to provide reference values for stiffness, muscle tone, relaxation periods and elasticity of various muscles in patients with non-myotonic neuromuscular disorders, (3) assess correlations between to compare result values for stiffness, muscle tone, relaxation periods and elasticity with clinical muscle function tests, measured by clinical evaluation (MRC-scale) and the 6-minute walk test; (4) assess correlations between subcutaneous fat and muscle thickness and echogenicity, measured by muscle ultrasound and result values for stiffness, muscle tone, relaxation periods and elasticity.

METHODOLOGY: This is a monocentric, blinded, cross-sectional explorative study in patients with neuromuscular diseases.

NUMBER OF PATIENTS: Approximately 70 patients will be enrolled, about 5 each in the following disease groups: Limb-Girdle-Muscular Dystrophy (LGMD), Myotonic Dystrophies Type 1 and 2 (DM1, DM2), Late-Onset-Pompe Disease (LOPD), Distal Myopathies, Congenital Myotonia, Spinal muscular atrophy Type 3 (SMA3), Amyotrophic lateral sclerosis (ALS) and peripheral Polyneuropathies (CIDP, HMSN). Approximately 20 healthy age- and gender-matched patients will be enrolled as a control group.

INCLUSION/EXCLUSION CRITERIA:

Inclusion Criteria: A patient must meet all of the following criteria to be eligible for this study. For patients, (1) the participant is ≥ 18 years of age and has a confirmed neuromuscular disease, (2) provides written consent and (3) is able and willing to perform study procedures. For healthy volunteers, age ≥ 18 and written informed consent is obligatory and there is no clinical sign for any neuromuscular disorder.

Exclusion Criteria: If one of the following criteria is met, a patient will not be able to participate in this study: (1) The patient has severe comorbidities; (2) the patient is participating in another clinical study using investigational treatment; (3) the patient cannot perform required muscle function tests; (4) the patient, in the opinion of the Investigator, is unable to adhere to the requirements of the study.

REGIMEN/STUDY PROCEDURES:

After obtained informed consent, the following procedures will be performed:

- at screening, patient's eligibility will be defined.

- at visit 1 (same day as Screening), the following procedures will be performed: (1) Collection of demographic and disease-related data (age, gender, diagnosis, age at onset of symptoms, age at diagnosis, severity and location of myotonia and severity and location of muscle stiffness, for both using numeric rating scale (NRS)). (2) Performing a 6-Minute-Walk-Test (meters). (3) Clinical evaluation of muscle strength of the following muscles, using the MRC-Scale (0-5): on both sides thenar and hypothenar, m. biceps brachii, m. triceps brachii, m. deltoideus, m. quadriceps femoris, m. tibialis anterior and gastrocnemius muscles. (4) Semiquantitative measurement of cutis and subcutis, subcutaneous fat and muscle thickness by muscle ultrasound of the following muscles: on both sides thenar and hypothenar, m. biceps brachii, m. triceps brachii, m. deltoideus, m. quadriceps femoris, m. tibialis anterior and gastrocnemius muscles. Measurements will contain thickness of cutis in millimeters, the thickness of subcutaneous fat in millimeters, muscle thickness in millimeters at the point of measurement of the MyotonPro® and semiquantitative measurement of muscle echogenicity, using Heckmatt scale I-IV. (5) Measurement of relaxation time, stiffness and elasticity of the following muscles, using the MyotonPro® device: on both sides thenar and hypothenar, m. biceps brachii, m. triceps brachii, m. deltoideus, m. quadriceps femoris, m. tibialis anterior and gastrocnemius muscles. For the documentation of the results, please see section "MyotonPro® device".
- at Visit 2 (+1-7 days after day 1), a measurement of relaxation time, stiffness and elasticity of the following muscles, using the MyotonPro® device: on both sides thenar and hypothenar, m. biceps brachii, m. triceps brachii, m. deltoideus, m. quadriceps femoris, m. tibialis anterior and gastrocnemius muscles will be performed for reliability purposes. For the documentation of the results, please see section "MyotonPro® device".

STATISTICAL METHODS:

All patients who participate in this study will be included in the analysis. Data collected in this study will be reported using summary tables, figures and patient data listings. Summary statistics (n, mean, median, standard deviation, minimum and maximum) will be calculated for the continuous variables and shift tables and/or frequencies, and percentages will be produced for the categorical variables. Due to the exploratory nature of this study, no formal inferential statistical tests will be performed.

4 BACKGROUND

In neuromuscular diseases, muscular involvement is extremely heterogeneous. The high variability is not only present in various neuromuscular diseases, but also within one type of disease itself. Since phenotypes vary among affected patients, a long delay between the onset of symptoms and diagnosis is common in neuromuscular disorders [1]. In myotonic dystrophies, specific muscles are affected by myotonia and stiffness, whereas other muscles or muscle groups may not or only be slightly affected or may show signs of weakness and atrophy [2]. In non-dystrophic myotonia like congenital myotonia Becker and Thomson, a generalized muscles stiffness is present in almost all patients at younger ages. For dystrophic and non-dystrophic myotonia, hallmarks are a delayed relaxation and stiffness of affected muscles after voluntary contraction [3, 4], but phenotypes show high variability. Non-invasively, myotonia and muscle stiffness is typically only described clinically, but not objectively measured. Semi-invasively, the severity of myotonia can be assessed by electromyography, requiring a high logistic and technical effort including sophisticated computerized measurements, which makes implementation in clinical practice almost impossible. In several Limb-girdle-muscular dystrophies (LGMD), muscles are selectively affected by fatty infiltration and atrophy. This becomes most evident in autosomal recessive LGMD2L, where the medial gastrocnemius muscles are selectively affected by fatty infiltration and atrophy at early stages of the disease, while proximal muscles are more likely to cause myalgia and reduced muscular endurance, but do not show signs of fatty infiltration [5]. In Late-Onset Pompe disease (LOPD), abdominal and paraspinal muscles are early and primarily affected [6-8]. In contrast, affection of the second motoneuron (Amyotrophic lateral sclerosis (ALS); spinal muscular atrophy (SMA)) as well as diseases with affection of the peripheral nervous system (chronic inflammatory demyelinating polyneuropathy (CIDP) or different forms of hereditary sensory and motor neuropathies (HMSN)) cause muscular atrophy without signs fatty infiltration, but are associated with muscular cramps in the majority of cases [9-12]. For assessing fatty infiltration of muscles or muscular atrophy, magnetic resonance imaging (MRI) is increasingly used as a complement to clinical and electrophysiological examination in neuromuscular disease, but costs and time are limitations [13]. Muscle ultrasound has proven to have a high sensitivity and specificity for characterizing and detecting neuromuscular disorders but is always complementary to clinical and electrophysiological findings [14]. It may be useful to detect and describe muscular movements like fasciculations and myokymia, but a correlation of myotonia or muscle stiffness with clinical disease severity is poor [15, 16].

To assess myotonia and muscle stiffness in neuromuscular disorders, we use a handheld device that allows non-invasive measurement of relaxation time, stiffness and elasticity. For this, the MyotonPro®, a commercially available device, is used to evaluate the stiffness, myotonia and elasticity of muscle fibers by applying short pulses to the underlying tissue [17]. Its validity and reliability were proven in a large cohort

of healthy volunteers as well as patients with different types of muscle diseases [17-22]. A brief pulse of a few seconds causes the underlying tissue to oscillate and send back a signal that is picked up and processed by the device. This allows to evaluate relaxation time, stiffness and elasticity of the tissue and may help to assess the severity of myotonia and stiffness in neuromuscular patients. The following measurements will be performed automatically, analyzing the oscillation curves and calculating the tissue tone (frequency (Hz)), the tissue stiffness (N/m), the decrement as parameter for the elastic stiffness of the tissue and viscoelastic parameters like relaxation time (in milliseconds) and creep as non-elastic tissue strain. The device has recently been used in patients with altered muscle elasticity and stiffness like Parkinson's disease, stroke and Duchenne muscular dystrophy [19-21, 23-25] as well as assessing muscular atrophy and viscoelasticity due to immobility in healthy subjects [22].

So far, the knowledge of muscle elasticity, myotonia and stiffness in various neuromuscular diseases is scarce. The study aims to test elasticity, myotonia and stiffness in various neuromuscular diseases and to provide reference values for different neuromuscular disease groups.

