5.2 Secondary Objectives

The secondary objectives of this study are

- to provide reference values for stiffness, muscle tone, relaxation periods and elasticity of various muscles in patients with dystrophic or non-dystrophic myotonia,
- to provide reference values for stiffness, muscle tone, relaxation periods and elasticity of various muscles in patients with non-myotonic neuromuscular disorders,
- assess correlations between to compare result values for stiffness, muscle tone, relaxation periods and elasticity with clinical muscle function tests, measured by clinical evaluation (MRC-scale) and the 6-minute walk test,
- assess correlations between subcutaneous fat and muscle thickness and echogenicity, measured by muscle ultrasound and result values for stiffness, muscle tone, relaxation periods and elasticity

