6.3 Number of patients

Approximately 70 patients will be enrolled, about 3-5 each in the following disease groups: Limb-Girdle-Muscular Dystrophy (LGMD), Myotonic Dystrophies Type 1 and 2 (DM1, DM2), Late-Onset-Pompe Disease (LOPD), Distal Myopathies, Congenital Myotonia, Spinal muscular atrophy Type 3 (SMA3), Amyotrophic lateral sclerosis (ALS) and peripheral Polyneuropathies (CIDP, HMSN). 20 healthy age- and gender-matched patients will be enrolled as a control group.

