10.2 Determination of Sample Size

50 patients and 20 healthy subjects will be enrolled in this study. No formal sample size calculations have been performed. This is an exploratory pilot-study and is not powered to make any statistical inferences.

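### The protocol names reference values in patient groups as a deliverable, but neither the disease groups nor, at the stated group sizes, the pooled classes are large enough to supply them

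*Protocol*

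**What the plan says.** **The aim.** Section 4 closes by saying the study aims "to provide reference values for different neuromuscular disease groups". Section 5.2 sets two secondary objectives, repeated in the synopsis. One is "to provide reference values for stiffness, muscle tone, relaxation periods and elasticity of various muscles in patients with dystrophic or non-dystrophic myotonia". The other has the same wording for "elasticity of various muscles in patients with non-myotonic neuromuscular disorders". Section 7.1.4 gives the working out of reference values as a purpose of the study, without naming a level.

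**The group sizes.** Section 6.3 reads "Approximately 70 patients will be enrolled, about 3-5 each" and then lists the diagnoses. The synopsis has "about 5 each in the following disease groups". The patient total is about 70 in the synopsis, 6.3 and 7.3, each with 20 controls in addition. It is 50, with 20 healthy subjects, in 7.1 and 10.2.

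**The limits the protocol sets itself.** Section 10.2 reports no sample size calculation and says the study "is not powered to make any statistical inferences". Section 10.1 plans n, mean, median, SD, minimum and maximum for continuous variables. Section 4 describes high variability both between diseases and within a single disease.

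**The concern.** A reference value is a statement about people outside the sample: it tells a later reader what to expect in another patient with the same condition. Section 10.2 disclaims that kind of statement, while sections 4, 5.2 and 7.1.4 name it as a product of the study. Pilot status explains the small groups, but it does not justify the label.

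Section 8.2 foresees the measurements helping with earlier diagnosis and with judging treatment effects. If summaries from a handful of patients are published as reference values for a disease, a large share of patients with that disease would lie outside them through sampling error alone.

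**Working it through.** **1. The protocol's own headcount.** There is no power-based figure to reproduce, so the check is groups times patients per group. The list in 6.3 can be read as 8 groups (myotonic dystrophy as one), 9 (DM1 and DM2 separate) or 10 (CIDP and HMSN also separate).

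- At 5 per group: 8 × 5 = 40, 9 × 5 = 45, 10 × 5 = 50. Ten groups of five reproduce the 50 patients of 7.1 and 10.2.
- At 3 to 5 per group the possible total is 8 × 3 = 24 to 10 × 5 = 50, so 70 patients is not reached. The figure 70 is reproduced only as 50 + 20 controls.
- If 70 patients were enrolled, the groups would hold 70/10 = 7 to 70/8 = 8.75 patients.

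**2. Formulas.** The protocol gives no SD, so results are in SD units.

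- Expected share of the population inside the observed minimum to maximum: (n−1)/(n+1). This needs only a random sample from a continuous distribution.
- 95% CI for the SD, as a multiple of the estimate: √[(n−1)/χ²(0.975, n−1)] to √[(n−1)/χ²(0.025, n−1)]. Assumes normal data.
- Half-width of the 95% CI for the mean: t(0.975, n−1)/√n. Assumes normal data.

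**3. Single disease groups.**

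| n | Min-max coverage | 95% CI for SD (× estimate) | Mean CI half-width (SD) |
|---|---|---|---|
| 3 | 2/4 = 50% | 0.52-6.28 | 2.48 |
| 5 | 4/6 = 67% | 0.60-2.87 | 1.24 |
| 7 | 6/8 = 75% | 0.64-2.20 | 0.92 |
| 9 | 8/10 = 80% | 0.68-1.92 | 0.77 |

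The rows n=7 and n=9 bracket the 70-patient reading. A mean ± 1.96 SD range does not rescue the small groups: simulated with normal data, it covers on average 77% at n=3 and 85% at n=5, and in the worst 5% of samples no more than 28% and 53%.

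**4. Pooled classes of section 5.2, at 3 to 5 per group.**

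- Myotonic (DM1, DM2, congenital myotonia): 3 × 3 = 9 to 3 × 5 = 15 patients. Coverage is 8/10 = 80% to 14/16 = 88%.
- Non-myotonic (6 or 7 groups): 6 × 3 = 18 to 7 × 5 = 35 patients. Coverage is 17/19 = 89% to 34/36 = 94%.
- Healthy controls: n=20. Coverage is 19/21 = 90%.
- Expected coverage of 95% needs (n−1)/(n+1) = 0.95, so n = 39. No set reaches it.

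With 70 patients spread evenly over ten groups of 7, the myotonic class would have 21 (20/22 = 91%) and the non-myotonic class 49 (48/50 = 96%). The latter passes the mark on average, but only for a mixture of diseases in the proportions enrolled.

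**The case against.** The best defence is that the operative objectives in 5.2 are already written for two broad classes, that 7.1.4 names no level, and that only one Background sentence speaks of disease groups. This stands in part. A reader might infer that the protocol promises a reference range for each diagnosis separately. That reading combines section 4 with 6.3, which uses the same term for its list of diagnoses; neither section 4 nor 5.2 says it outright. What the text shows is an aim stated at two levels, and the group sizes fall short at both.

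A second defence is that no section prescribes a minimum-maximum or mean ± 2 SD reference range, or uses one to classify patients, and that the derivation may be left to an analysis plan. The first part is correct: the coverage figures measure what the sample can carry and do not describe a planned calculation. But the aim is protocol content, and no analysis method can turn 3 to 5 patients into a reference for a disease.

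A reader might also infer that pooling solves the problem. The documents do not support this. At 3 to 5 per group both classes stay below 95%. Section 4 contrasts limb-girdle dystrophies with fatty infiltration against motor neuron and nerve disorders with atrophy but without it. The limits of a pooled non-myotonic range would depend on how many of each were enrolled, so it would be a reference for no single disease.

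Finally, the n=3 figures are the least favourable reading of disputed group sizes. That is true, and it is why n=5, 7 and 9 are shown alongside.

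**Conclusion.** The deliverable is wrong as written. Reference values in patient groups are not something this design can produce, and the wording conflicts with section 10.2. For a single disease, expected coverage is 50% to 67% at 3 to 5 patients and only 75% to 80% if 70 patients are enrolled, so the conclusion does not depend on which total is right. The pooled classes are better but insufficient at the stated group sizes, and they are heterogeneous.

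The coverage figures assume random sampling from one continuous distribution; the SD and mean figures also assume normality. Recruitment at one centre during routine care, and the mixing of diseases in the pooled classes, make the first assumption generous. Descriptive use of the data is not in question.

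**What to change.** - In the synopsis and sections 4, 5.2 and 7.1.4, replace reference values in patients with preliminary descriptive values, and align the level named in section 4 with 5.2.
- For each disease, report the individual values (listings are already planned in 10.1 and 10.5) and add the mean with its 95% CI.
- Label any pooled or control-group range as preliminary and show confidence limits for its bounds. Do not present pooled patient ranges as reference intervals.
- Reconcile the group size (3 to 5 against about 5) and the patient total (50 against 70) across the synopsis, 6.3, 7.1, 7.3 and 10.2.

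The cost is an amendment to the wording, a few table columns and a less ambitious stated aim. No extra patients or measurements are needed.

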5 STUDY OBJECTIVES

5.1 Primary Objective

The primary objective of this study is to assess stiffness, muscle tone, relaxation periods and elasticity of various muscles in patients with dystrophic or non-dystrophic myotonia.

5.2 Secondary Objectives

The secondary objectives of this study are

- to provide reference values for stiffness, muscle tone, relaxation periods and elasticity of various muscles in patients with dystrophic or non-dystrophic myotonia,
- to provide reference values for stiffness, muscle tone, relaxation periods and elasticity of various muscles in patients with non-myotonic neuromuscular disorders,
- assess correlations between to compare result values for stiffness, muscle tone, relaxation periods and elasticity with clinical muscle function tests, measured by clinical evaluation (MRC-scale) and the 6-minute walk test,
- assess correlations between subcutaneous fat and muscle thickness and echogenicity, measured by muscle ultrasound and result values for stiffness, muscle tone, relaxation periods and elasticity

6. STUDY POPULATION

6.1 Inclusion Criteria

A patient must meet all the following criteria to be eligible for this study. For patients, (1) the participant is ≥ 18 years of age and has a confirmed neuromuscular disease, (2) provides written consent and (3) is able and willing to perform study procedures. For healthy volunteers, age ≥ 18 and written informed consent is obligatory and

there is no clinical sign for any neuromuscular disorder.

6.2 Exclusion Criteria

If one of the following criteria is met, a patient will not be able to participate in this study: (1) The patient has severe comorbidities; (2) the patient is participating in another clinical study using investigational treatment; (3) the patient cannot perform required muscle function tests; (4) the patient, in the opinion of the investigator, is unable to adhere to the requirements of the study.

6.3 Number of patients

Approximately 70 patients will be enrolled, about 3-5 each in the following disease groups: Limb-Girdle-Muscular Dystrophy (LGMD), Myotonic Dystrophies Type 1 and 2 (DM1, DM2), Late-Onset-Pompe Disease (LOPD), Distal Myopathies, Congenital Myotonia, Spinal muscular atrophy Type 3 (SMA3), Amyotrophic lateral sclerosis (ALS) and peripheral Polyneuropathies (CIDP, HMSN). 20 healthy age- and gender-matched patients will be enrolled as a control group.

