7 INVESTIGATIONAL PLAN

7.1 Study Design

This is a cross-sectional, blinded, monocentric, explorative study to evaluate the stiffness, muscle tone, relaxation periods and elasticity of various muscles in patients with neuromuscular diseases. Local ethic's approval is obligatory before the recruitment of the first patient. The patient must provide informed consent prior to performing any protocol-related procedure at the screening visit. The estimated duration of this study is 12 months or as soon as a total of 50 patients with neuromuscular diseases and 20 healthy volunteers are evaluated. The person assessing the muscle stiffness and myotonia, using the MyotonPro® device, will be blinded to the diagnosis, to medical history as well as results from the clinical tests (clinical muscle strength, 6-minute-walk-test) and results of muscle ultrasound assessments. The study duration for one patient or one healthy volunteer is two to a maximum of seven days. All relevant data will be assessed within visit 1. At the second visit (visit 2), only measurements of the MyotonPro® will be repeated to evaluate the reliability of the measurements.

Both patients and healthy volunteers will perform the following assessments:

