7.2.2 Premature Patient Discontinuation from the Study

Patients are free to withdraw consent and/or discontinue participation in the study at any time, without prejudice to further treatment. For patients who prematurely discontinue from the study, the Investigator or designee will contact the patient 4 to 7 days after withdrawal to assess any AEs. Post-study serious adverse events (SAEs) will be reported accordingly. A patient's participation in the study may also be discontinued at any time at the discretion of the Investigator. Patients who are prematurely withdrawn from the study will be asked to complete all discontinuation assessments prior to withdrawal, if possible. A patient will be considered early terminated if the patient does not complete the study after enrollment. Patients who are withdrawn from the study will not be replaced (i.e., a patient's study number will not be reused); however, additional patients may be enrolled to offset patient dropouts.

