7.3 Discussion of Study Design, Including Choice of Control Group

This is a monocentric, blinded, cross-sectional explorative study designed to evaluate myotonia, muscle stiffness and elasticity in 70 patients with neuromuscular disorders. For statistical comparison, we plan to recruit 20 healthy subjects as a control group.

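### The protocol gives two patient numbers (about 70 and 50) and two group sizes (about 5 and 3-5), and its disease groups cannot yield 70 diseased patients

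*Protocol*

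**What the plan says.** The numbers appear in five places in the protocol.

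- **Synopsis:** "Approximately 70 patients will be enrolled, about 5 each in the following disease groups". A separate sentence follows: "Approximately 20 healthy age- and gender-matched patients will be enrolled as a control group".
- **Section 6.3:** "Approximately 70 patients will be enrolled, about 3-5 each in the following disease groups", followed by "20 healthy age- and gender-matched patients will be enrolled as a control group".
- **Section 7.1:** the estimated duration is "12 months or as soon as a total of 50 patients with neuromuscular diseases and 20 healthy volunteers are evaluated".
- **Section 7.3:** the study is "designed to evaluate myotonia, muscle stiffness and elasticity in 70 patients with neuromuscular disorders". The next sentence reads: "For statistical comparison, we plan to recruit 20 healthy subjects as a control group".
- **Section 10.2:** enrolment is set at 50 patients plus 20 healthy subjects, with no formal sample size calculation.

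The disease list is the same in the synopsis and in section 6.3: LGMD, myotonic dystrophy (DM1, DM2), LOPD, distal myopathies, congenital myotonia, SMA3, ALS and polyneuropathies (CIDP, HMSN). Neither place says how many groups this is meant to be.

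**The concern.** Section 7.3 and section 10.2 give different numbers of diseased patients for the same study, 70 and 50. The synopsis and section 6.3 attach the figure of 70 directly to the disease list, yet the quotas stated beside it do not add up to 70. The two quotas also differ from each other.

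The number of people to be enrolled is part of what the ethics committee approves, and it tells the site when recruitment is complete. A site working to 7.1 would finish at 50 patients and miss 7.3 by 20. A site working to 7.3 would enrol 20 more patients than 10.2 provides for.

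Group size matters for a second reason. Two of the secondary objectives are reference values for myotonic and for non-myotonic disease, and the primary objective concerns myotonic patients only. The quotas and the definition of a group fix how many patients stand behind those results.

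**Working it through.** **Inputs.** Group size is 3-5 (section 6.3) or about 5 (synopsis). Controls are 20 in all five places. The number of groups is counted from the list: 8 if DM1/DM2 and CIDP/HMSN are each one group, 9 if one pair is split, and 10 if both are.

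**Totals as worded.**
- Section 7.3: 70 + 20 = 90 participants.
- Sections 7.1 and 10.2: 50 + 20 = 70 participants.
- Difference in patients: 70 − 50 = 20, and 20/70 = 29%.

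**Diseased patients from the list** (number of groups × patients per group):

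| Groups | 3 each | 4 each | 5 each | 5 each plus 20 controls |
|---|---|---|---|---|
| 8 | 24 | 32 | 40 | 60 |
| 9 | 27 | 36 | 45 | 65 |
| 10 | 30 | 40 | 50 | 70 |

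- The figure of 50 in sections 7.1 and 10.2 is reproduced in one cell only: 10 × 5 = 50.
- The figure of 70 as diseased patients, as in section 7.3, is not reproduced in any cell. The highest count is 50, which is 70 − 50 = 20 short (29% of 70). The lowest is 24, which is 70 − 24 = 46 short (66%).
- The figure of 70 is reproduced only as a participant total: 10 × 5 + 20 = 70.

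**What 70 diseased patients would need.**
- Ten groups: 70/10 = 7 each, and 7/5 = 1.40, so 40% above the stated upper limit of 5.
- Eight groups: 70/8 = 8.75 each, and 8.75/5 = 1.75, so 75% above it.
- At 5 per group: 70/5 = 14 groups.

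**What 50 diseased patients would need.** Ten groups: 50/10 = 5 each. Eight groups: 50/8 = 6.25 each, which is also above the limit.

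**Myotonic patients for the primary objective.** With DM1/DM2 as one group plus congenital myotonia: 2 × 3 to 2 × 5 = 6-10. With DM1 and DM2 separate: 3 × 3 to 3 × 5 = 9-15.

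**Dropout.** Section 7.2.2 says that "additional patients may be enrolled to offset patient dropouts", which might suggest 70 enrolled to give 50 evaluated. But 10.2 gives 50 as the number to be enrolled, 7.2.2 gives no allowance, and the controls carry no surplus in any section.

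**The case against.** The best defence is that 70 is the total headcount. The synopsis and section 6.3 call the healthy controls patients too, so about 70 patients can include them. Then 50 + 20 = 70, and both places agree with 7.1 and 10.2. On that reading four of the five places are consistent, and the only clear error is one phrase in 7.3, probably a total carried over as a patient count. The shortfall against the disease list then follows from that slip and is not a separate defect.

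Much of this stands. Taken alone, 6.3 and the synopsis are ambiguous and not contradictory. The 66% shortfall combines the fewest groups, the smallest quota and the reading least favourable to the plan; the solid figure is 20 patients. The gap between about 5 and about 3-5 is minor on its own, since both are approximate and overlap. Section 7.1 speaks of an estimated duration, not a strict recruitment rule. Correcting 7.3 alone would not settle the number of myotonic patients. The study is an exploratory pilot with no power calculation, so the consequences are limited.

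What does not stand is that the plan can be left as it is. Section 7.3 specifies neuromuscular disorders and adds the 20 healthy subjects separately, so it cannot be read as a total. Qualifiers such as about do not cover a gap of 20 patients, and the figures in 7.1, 7.3 and 10.2 carry no such qualifier for the patient number.

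**Conclusion.** The concern holds. Section 7.3 contradicts 7.1 and 10.2 by 20 patients (70 against 50), or 90 against 70 participants. The synopsis and 6.3 do not resolve this, because they place the 70 next to a disease list that yields 24 to 50 patients. The two group sizes differ, and the 3-5 range in 6.3 fits the target of 50 only at its upper end.

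The result rests on one assumption, that the list means eight to ten groups. The conclusion does not depend on which count is chosen, since even ten groups of five fall 20 short of 70. That 70 was meant as the participant total is an inference, the only one under which the quotas, 7.1 and 10.2 agree; the sponsor should confirm it. No stated power or inference is affected. A conflicting enrolment number should still be corrected before recruitment relies on it.

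**What to change.** State one plan in the synopsis and in sections 6.3, 7.1, 7.3 and 10.2, for example: *70 participants in total: 50 patients with neuromuscular disease, in ten groups of about 5 (DM1, DM2, CIDP and HMSN each counted as a group), and 20 healthy controls.*

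- In section 7.3, replace 70 with 50 as the number of diseased patients.
- In the synopsis and 6.3, use participants for the total and keep patients for those with disease.
- In 6.3, replace the 3-5 range with about 5. At 3 or 4 per group, ten groups give 30 or 40 patients, not 50.
- Naming the ten groups also fixes the myotonic patients at about 15 (3 × 5).

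**Cost.** This is a change of wording only, but under section 12.2 it needs an amendment signed by the investigator and approved by the ethics committee. If 70 was always the total, planned enrolment does not change. Measured against 7.3 as written, the stated patient number falls by 20. Should the sponsor really intend 70 diseased patients, 7.1 and 10.2 would have to change instead, the quotas would have to rise to about 7 in each of ten groups, and 20 more patients would have to be recruited than those sections foresee.
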